“Prevention of OUD: The HOME (Housing, Opportunities, Motivation and Engagement) Randomized Trial”

NCT04135703

6/28/2024

Study Protocol

Overview of Design

240 homeless youths between the ages of 18 to 24 years recruited from the streets and drop-in center/shelters will be randomly assigned to 1) 6-months of housing + opioid and related risk prevention services (n = 120), or to 2) opioid and related risk prevention services alone (n = 120). Using an intent to treat design, follow-up assessments will be completed at 3, 6, 9 and 12 months post-baseline. Upon completion of the baseline assessment interview, youths will be randomly assigned to the intervention conditions using a computerized urn randomization program. Four advocates will provide services so that advocate effects can be examined (Baldwin et al., 2011), and each advocate will provide all opioid and related risk prevention services to the youth on their caseload. Advocates will be crossed by condition to “equate” conditions on advocate characteristics.

Sample Inclusion Criteria.

1. Youth were between the ages of 18 to 24 years. Our experience is that landlords will not accept leases signed by youth ages 16-17 years. “Homeless youth” commonly refers to those up to the age of 24 years (Robertson & Toro, 1999; USICH, 2010), thus, this age range generally reflects the age range of the homeless youth population served by providers across the country.
2. Youth met the criteria for homelessness as defined by the federal McKinney-Vento Act (2002) as “lacking a fixed, regular, stable, and adequate nighttime residence” and includes “living in a publicly or privately operated shelter designed to provide temporary living accommodations, or a public or private place not designed for, or ordinarily used as, regular sleeping accommodations for human beings.”
3. Youth failed to meet DSM 5 criteria for Opioid Use Disorder as assessed by the SCID (First et al., 2015).

Screening and intake. Project staff maintain offices within the drop-in center. An RA engaged and screened youth to determine basic eligibility for the study. After the brief screening and stated interest in the project, written consent was obtained and the Structured Clinical Interview for DSM-5 Disorders (SCID) (First, Williams, Karg, & Spitzer, 2015) section on Opioid Use Disorder, was administered to determine formal eligibility.

Project Intervention: Opioid and Related Risk Prevention Services

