Housing + Opioid and Related Risk Prevention Services integrates independent housing, Strengths-Based Outreach and Advocacy (SBOA), HIV prevention and MI (Miller & Rollnick, 2012). In the housing + opioid and related risk prevention services condition, youth will be housed in an apartment of their choosing and receive six months of utility and rental assistance of up to \$600 per month. The independent housing is not contingent on the youth’s substance use or attendance in prevention services. SBOA, MI and HIV risk prevention occur simultaneously in this approach. Addressing basic needs but not opioid and other drug use, through MI and service linkage, may lead to difficulty in maintaining basic needs and vice versa. During the intervention, advocates assist youth in accessing community supports so that if more assistance is needed at the end of the intervention period, youth will have been linked to those additional supports. Findings from the pilot study with non-service connected youth indicated that up to 26 advocacy sessions should be offered. Each component of the intervention is described below.

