Motivational Interviewing (MI). Typically offered as a brief intervention of 1-2 sessions, Motivational Interviewing (MI, Miller & Rollnick, 2012) has a strong record of efficacy in the prevention and treatment of alcohol and other drug use disorders (Copeland et al., 2015; Miller & Rollnick, 2012). MI assumes that the responsibility and capability for change lie within the client and needs to be evoked (rather than created or installed). Baer, Peterson and Wells (2004) provide some rationale for utilizing brief feedback and motivational intervention with street living youth - the intervention is less costly and demands much less of a hard-to-reach population than more intensive interventions. Utilizing a sample of runaway adolescents recruited from a runaway shelter, Slesnick et al. (2013) found that substance use reductions were significant for those assigned to MI even to two years post-treatment. The advocate will administer MI. Four principles guide the practice of MI: express accurate empathy, develop discrepancy, roll with resistance and support self-efficacy. The Project Match manual was adapted for homeless/runaway youth in prior trials in consultation with [name] and [name] (NIAAA grant no. R01AA12173 and NIDA grant R29DA11590). Adaptation of the manual included attention to the unique life situation of homeless youth in understanding motivations and challenges to recovery while homeless. Session 1 begins with a period of open-ended MI, to establish therapeutic rapport and elicit client change talk. In session 2 the advocate continues to focus on enhancing intrinsic motivation for change, developing discrepancy, transitioning as appropriate into the negotiation of a change plan and evoking commitment to the plan.

Housing + Opioid and Related Risk Prevention Services. Those randomized to receive housing + opioid and related risk prevention services will receive all the above and also receive 6-months of rental and utility supports in an apartment of their choosing.

All youth completed a **baseline and follow-up assessment** which included self-report, interview, and physiological measures, with the following outcomes.

Primary Outcomes: **1)** time to OUD (SCID) (UH3) **2)** % days opioid use (Form 90) (UG3, UH3).

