Secondary Outcomes: **1)** % days other alcohol/drug use (Form 90), **2)** drug use consequences (SIP) **3)** HIV risk score (0-7) **4)** % days housed (Form 90), **5)** BDI-II depression score, **6)** Physical health score (SF-6), **7)** % days employed and % days in school/training (Form 90), **8)** resilience score (BRS), **9)** coping (task, emotion and avoidance) scores (CISS) **10)** cognitive distortions score (CD-QUEST), and **11)** self-regulation score (SSRS).

Mediators: Primary: **1)** # of service contacts (service log), **2)** working alliance score (WAI), **3)** social support (SNI): number and satisfaction of support persons, and **4)** # of violence/victimization exposures (HEQ).

Secondary: **1)** Stress (2 dv's) self-reported stress score (Cohen's PSS), and physiological hair cortisol level, and **2)** Self-efficacy (3 dv's): HIV, substance use, and perceived personal control scores.

Study Aims were as follows:

Specific Aim 1. Evaluate the relative efficacy of housing + opioid and related risk prevention services compared to prevention services alone (N = 240). Hypothesis. Youth receiving the 6-month housing + prevention services will show better 3, 6, 9 and 12 month outcomes than those receiving prevention services alone. Fewer Housing First youth will progress to OUD and will be more likely to remain housed at one year.

Specific Aim 2. Test the effects of the primary and secondary mediators on the primary outcome (opioid use/time to OUD) and secondary outcomes. Hypothesis. Inasmuch as the intervention triggers

successful social micro and meso-system interactions or social resources (e.g., advocate and social service meetings), individual resources will be activated – e.g., stress will decrease and self-efficacy will increase, leading to multiple positive outcomes.

Specific Aim 3. Explore how moderators affect individual's response to housing + opioid and related risk prevention services.

Statistical Analysis Plan

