Missing Data. The patterns of missing data will be first examined before each analysis. If data are missing at random, they will be estimated using full information maximum likelihood (FIML) or multiple imputations (MI) method. When data are missing completely at random (MCAR) or are missing at random (MAR), both FIML and ML produce unbiased results (Enders, 2010). The main statistical program used for this study, MPlus, can handle missing data by providing FIML estimation. If the missingness cannot be explained by observed data, that is, data are Missing Not at Random (MNAR), data analysis will be conducted using the pattern mixture model (Roy, 2003) framework.

Study Aim 1. The impact of the two intervention conditions (i.e., 6-months housing + opioid and related risk preventive services, and opioid and related risk preventive services alone) on the primary and secondary outcomes will be tested in Aim 1. Specifically, the primary outcome, time to the onset of OUD, will be analyzed using the discrete-time survival analysis. In this analysis, whether the onset of OUD has occurred at a specific time point is included as the indicator of a latent factor, the proportional odds for the hazard of OUD, which is predicted by the contrasts between conditions. It is expected that youth assigned to the housing + preventive services condition will have longer delay in the onset of OUD than those in the preventive services alone condition. For the primary outcome, % days opioid use, and secondary outcomes that are continuous variables, latent growth models (LGM) will be conducted to estimate the trajectories of change across five time points (baseline, 3, 6, 9 and 12 months follow-up) to estimate the trajectories of change over time. Differences between treatment conditions on estimated growth parameters, including intercepts (i.e., initial status) and slopes (i.e., the rates of change), will be tested. It is expected that those assigned to the 6-month housing + opioid and related risk prevention services group will show greater decreases in opioid use (for those using opioids), as well as greater improvement in secondary outcomes, and that these improvements will maintain for a longer period of time, compared to those assigned to prevention services alone. To increase validity of the conclusions drawn from the analysis, the number of intervention sessions and contacts with other service providers will be covariates in the LGM analyses.

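### The Aim 1 growth models compare randomised arms on pre-randomisation initial status and name no contrast for the visit-specific or maintenance hypotheses

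*Combined protocol and SAP*

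**What the plan says.** Under Study Aim 1, the SAP fits latent growth models to % days opioid use (a primary outcome) and the continuous secondary outcomes at baseline, 3, 6, 9 and 12 months. It then states: "Differences between treatment conditions on estimated growth parameters, including intercepts (i.e., initial status) and slopes (i.e., the rates of change), will be tested". Time to OUD has its own discrete-time survival analysis and is outside this point.

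The Overview of Design fixes the order of events: "Upon completion of the baseline assessment interview, youths will be randomly assigned to the intervention conditions". The intervention section says that in the housing arm "youth will be housed in an apartment of their choosing and receive six months of utility and rental assistance", so support covers half of the 12-month follow-up.

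The hypotheses are framed differently from the tests. Specific Aim 1 says that the housing arm "will show better 3, 6, 9 and 12 month outcomes" and "will be more likely to remain housed at one year". Study Aim 1 in the SAP adds the expectation that "these improvements will maintain for a longer period of time".

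No growth shape, piecewise term, visit contrast or month 6 to 12 contrast is given for Aim 1. The Statistical Power Analysis gives .86 for the growth rate only.

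**The concern.** There are three gaps.

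1. **Initial status is fixed before treatment.** The intercept is defined as initial status and is measured before allocation. A between-arm test of it can reject only by chance or because the curve is misspecified. Neither is evidence about housing.
2. **The hypotheses have no matching test.** A slope difference answers the visit-specific hypotheses only if the effect is linear from a common baseline, which the plan does not say. Even then it does not address maintenance after rent support ends. Study Aim 2 uses 6-month and 9/12-month outcomes, but for indirect effects.
3. **The efficacy parameter is not fully defined.** Without a growth shape, the meaning of the slope for a primary outcome is open.

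At stake are some power, a possible significant initial-status difference that is really a treatment effect in the wrong place, and a maintenance claim with no planned estimate.

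**Working it through.** **Stated power.** The plan gives a coefficient of .15, N = 240, 15% attrition and power .86. It gives no alpha and no growth-model variances, so the figure cannot be uniquely reproduced. For a linear model over five waves (t = 0 to 4), the variance of the slope difference is (4/n)(ψs + σ²/10), where ψs is the slope variance, σ² the residual variance and 10 = Σ(t − 2)². Two-sided .05 is assumed throughout.

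- ψs = .10, σ² = .25, n = 204 completers: SE = √(4/204 × .125) = .0495; .15/.0495 = 3.03; power = Φ(3.03 − 1.96) = .858.
- ψs = .09, σ² = .5, n = 240: SE = √(4/240 × .14) = .0483; power .874.

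Over wider assumed variances, power runs from .50 to .99. The .86 is attainable and is not shown to be wrong.

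**Illustration inputs (assumed).** Intercept variance .5, residual variance .5 (so baseline SD = 1), ψs = .10 or .03 per wave, zero intercept-slope correlation unless stated, n = 220 with complete data, normal outcomes. The session and service-contact covariates are not modelled.

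**Standard errors, free intercepts.**
- Slope: √(4/220 × .15) = .0522, or √(4/220 × .08) = .0381.
- Intercept: √(4/220 × (.5 + .5 × (1/5 + 4/10))) = √(4/220 × .8) = .1206.

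**Calibration.** The peak effect E is set so that a linear effect has power .86: E = 4 × (1.960 + 1.080) × SE = .635 or .464. Because E scales with the SE, the powers below do not depend on the choice of n.

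**Equal baselines.** The covariance of the fitted intercept and slope is −(4/220) × .1. Constraining the intercept difference to zero therefore makes the estimator slope + (.1/.8) × intercept. Its variance is (4/220)(ψs + .05 − .1²/.8), giving SE = .0500 or .0350.

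**Effect profiles at months 0, 3, 6, 9, 12, in units of E.** The fitted slope is Σ(t − 2)d/10 and the fitted intercept is mean(d) − 2 × slope.
- Linear (0, .25, .5, .75, 1): slope .25, intercept 0.
- Held (0, .5, 1, 1, 1): slope .25, intercept .70 − .50 = .20.
- Half lost (0, .5, 1, .75, .5): slope .125, intercept .55 − .25 = .30.

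With equal baselines, the slope becomes .25, .25 + .125 × .20 = .275, and .125 + .125 × .30 = .1625.

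| Profile | Slope power, free intercepts | Slope power, equal baselines | Initial-status test rejects |
|---|---|---|---|
| Linear | .86 | .89-.91 | .05 |
| Built to month 6, held | .86 | .94-.95 | .12-.18 |
| Half lost by month 12 | .33 | .54-.58 | .21-.35 |

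Example, half lost with ψs = .10: .1625 × .635/.0500 = 2.06, so power = Φ(2.06 − 1.96) = .54. The intercept is .30 × .635 = .191, and .191/.1206 = 1.58, which rejects in .35.

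For intercept-slope correlations from −.3 to +.3, the gain from equal baselines under a linear effect runs from about 0 to 9 points.

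**Maintenance contrast.** With free visit means and equal baselines, the change in arm difference from month 6 to month 12 has SE .160 or .143. A loss of half the effect is .318 or .232, so power is about .51 or .37.

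**The case against.** The strongest reply has four parts.

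**The intercept test is harmless.** Nothing in the plan presents initial status as evidence of efficacy, the stated expectations concern change, and power is quoted only for the growth rate. Under a linear effect the free intercept costs only 3-5 points at zero correlation, and almost nothing in some settings. This stands as a limit on size. It does not rescue the test, which has no treatment question to answer and misleads even when the effect is fully held.

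**The slope may be adequate.** If the effect is linear from equal baselines, a slope difference does imply a difference at every visit. That is correct, but the plan states neither condition.

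**Large losses are hypothetical.** A reader might infer that the planned test would miss an effect that fades once rent support ends. That needs both a single linear slope and fading, and the documents state neither. One slope is the natural reading of the Aim 3 and power text, but the plural use of slopes leaves others open. The wording "so that if more assistance is needed at the end of the intervention period" introduces a plan to link youth to further supports. It is not evidence of fading, and the SAP expects maintenance. The half-lost row is therefore a possibility only.

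**A joint test of months 6 and 12 is a preference.** A reader might infer that one is needed. It is not: it loses 5-7 points if the effect is linear (.80-.81 against .86). It also rejects in .96-.98 if the effect is held and .92-.99 if half is lost, so it cannot separate the two.

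**Conclusion.** The concern holds for the outcomes analysed by growth model. The initial-status comparison should go, and the growth shape and the contrasts that carry the Aim 1 hypotheses should be named. No other section of the plan supplies them.

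The gain from equal baselines is modest if the effect is linear (about 0 to 9 points over the correlations tried) and larger if it is not. It cost no power under any profile tabulated. These sizes rest on assumed variances, complete data and normality. Entry requires absence of OUD rather than opioid use, so % days opioid use may contain many zeros and its figures could differ. The logical points, that baseline precedes allocation and that the hypotheses lack matching contrasts, need no such assumption.

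This affects interpretation and some power for one primary outcome. It does not invalidate the trial, does not show the stated .86 to be wrong, and leaves time to OUD untouched.

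**What to change.** For % days opioid use and the continuous secondary outcomes:

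- **Baseline.** Constrain baseline means equal across arms and drop the between-arm test of initial status.
- **Shape and estimates.** Name the growth shape, allowing a change near month 6 or free visit means. From that model, report the arm differences at 3, 6, 9 and 12 months with confidence intervals, and the change in arm difference from month 6 to month 12 as the estimate of maintenance. State that this last estimate is imprecise (power about .37-.51 for loss of half the effect in the illustration).
- **Governing contrast.** Name one efficacy contrast for % days opioid use and restate power for it. The slope with equal baselines, the month-12 difference, or a joint test of months 6 and 12 are all defensible, and the choice is the sponsor's. Keep the Aim 3 moderator tests on the same parameter.
- **Timing.** The protocol describes the assessments in the past tense, so date the change and make it before the data are analysed by arm.

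The cost is SAP wording, a small change to the Mplus model and a new power run. Equal baselines cost no power. The joint test, if chosen, gives up 5-7 points when the effect is linear.

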Study Aim 2. To test the proposed behavioral change mechanisms (i.e., social and individual resources), a series of path analysis will be conducted. Specifically, we will first test whether the primary mediator (e.g., service connections, social support) or secondary mediator (e.g., self-efficacy, stress) assessed at the 3- or 6-month follow-up mediates the association between intervention and outcome at 6-month and 9/12-month follow-up, respectively. We expect that the intervention condition with the housing component will produce greater improvement in social/individual resources, which in turn will predict better outcomes. We will also estimate serial mediation models, in which both primary and secondary mediators are included (Figure 1), to test whether intervention first affects social resources, which then lead to changes in individual resources and subsequent outcomes. In these models, the baseline assessment of the mediators and outcomes will be controlled for in the analysis. Following MacKinnon and colleagues (MacKinnon et al., 2007), the product of the coefficient of the path from the independent variable to the mediator(s) and the coefficient of the path from the mediator(s) to the outcomes will be computed as the indirect (mediation) effect between the intervention and outcomes. The strength and significance of the mediation will be estimated using a bootstrap sampling method (Shrout & Bolger, 2002).

Study Aim 3. The effect of the moderating variables (age, sex, race/ethnicity, sexual orientation, childhood abuse history, and baseline substance use and service connection) will be tested by examining the interaction between intervention type and each moderator in predicting outcome slopes in the growth models and survival analysis. The contrast between intervention conditions will be multiplied by each moderator variable to form an interaction term. Next, the interaction terms will be included in the analyses for Aim 1 for the primary/secondary outcomes, one at a time, and their strength of association with the outcome slope will be assessed while controlling the direct effects of the predictors on outcome and the direct effect of moderator variables on outcome. If the interaction term is significant, this suggests moderation.

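### The Aim 1 growth models adjust for sessions and service contacts, which arise after randomisation, so they do not estimate the effect of assignment

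*Combined protocol and SAP*

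**What the plan says.** - **Overview of Design.** The trial is described as "Using an intent to treat design". On timing: "Upon completion of the baseline assessment interview, youths will be randomly assigned to the intervention conditions". Sessions can therefore only accumulate after allocation.
- **Statistical Analysis Plan, Study Aim 1.** The growth models cover one primary outcome and the continuous secondary outcomes: "For the primary outcome, % days opioid use, and secondary outcomes that are continuous variables, latent growth models (LGM) will be conducted". The plan then adds that "the number of intervention sessions and contacts with other service providers will be covariates in the LGM analyses", giving as its reason: "To increase validity of the conclusions drawn from the analysis". No growth model without these covariates is specified, and the adjusted model is not labelled secondary, sensitivity or exploratory.
- **Mediators list.** The first primary mediator is the number "of service contacts (service log"). The Aim 2 hypothesis in the list of aims gives meetings with advocates and with social services as examples of the social resources that the intervention sets in motion.
- **Statistical Analysis Plan, Study Aim 2.** Service connections are tested as a mediator, and the direction is stated: "We expect that the intervention condition with the housing component will produce greater improvement in social/individual resources".

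**The concern.** Aim 1 asks how the two assigned conditions compare. Its growth models hold constant two quantities that assignment can change, and the plan's own theory says that it will change them. This has two consequences.

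First, whatever part of the housing effect works through engagement with advocates and services is removed from the condition coefficient. A real benefit can be adjusted away.

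Second, youths with the same number of contacts in the two arms are no longer comparable. Unmeasured traits such as motivation or severity drive both service use and outcome, and conditioning on contacts links those traits to arm. The adjusted coefficient then need not equal even the direct effect, and it can differ from zero when housing does nothing.

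The stated purpose is better validity; the adjustment works against it. Aim 3 adds its interaction terms to the Aim 1 analyses, so the problem carries into the moderator tests in the growth models as well.

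**Working it through.** **1. The plan's own power figure.** Statistical Power Analysis gives N = 240, 15% attrition, a coefficient of .15 on the slope and power .86. Alpha, sidedness and the growth-factor and residual variances are not stated, so .86 cannot be uniquely reproduced. At an assumed alpha of .05:
- Read as a standardised coefficient, .15 gives two-sided power of .64 (N = 240) or .57 (N = 204).
- Read as unstandardised in a linear five-wave model with 15% attrition, power runs from about .54 to .98 over slope variances of .05 to .20 and residual variances of .25 to .75. It is .865 to .875 at slope variance .05 with residual variance .75.

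The figure is attainable, so it is taken as the starting point.

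**2. Effect removed, by share mediated.** Power .86 at two-sided .05 means z = 1.96 + 1.08 = 3.04. If a fraction m of the effect runs through the covariates and the standard error is held fixed, power = Φ(3.04(1 − m) − 1.96).

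| m | z | power |
|---|---|---|
| 0 | 3.04 | .86 |
| .25 | 2.28 | .63 |
| .50 | 1.52 | .33 |
| .75 | 0.76 | .12 |

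**3. Effect removed, by path size, with the standard error recalculated.** With 120 × .85 = 102 per arm, power .86 corresponds to d = 3.04 × √(2/102) = .426. Let a be the arm's shift in contacts (SD units, assumed) and b the contacts-to-outcome coefficient. The plan assumes a medium size for b, and its largest quoted correlation is .46 in absolute value. Adjusted coefficient = .426 − ab. Its standard error is √(1 − b²) × √(2/102) / √(1 − R²), with R² = (a²/4)/(1 + a²/4).

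| a | b | adjusted coefficient | share removed | power |
|---|---|---|---|---|
| .2 | .3 | .366 | 14% | .78 |
| .3 | .3 | .336 | 21% | .70 |
| .5 | .46 | .196 | 54% | .33 |

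With a = 0 the adjusted and unadjusted effects coincide.

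**4. No true effect, unmeasured common cause.** Let housing shift contacts by s SD and have no effect on outcome. Let an unmeasured trait load l on both contacts and outcome, each with unit variance within arm. The adjusted arm coefficient is then biased by s × l². With n = 204, its standard error is √[(1 − l⁴) / (204 × .25 × (1 − R²))], where R² = (s²/4)/(1 + s²/4).

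| s | l | bias (SD) | SE | type I error |
|---|---|---|---|---|
| 0.2 | .5 | 0.05 | .136 | .07 |
| 0.5 | .4 | 0.08 | .142 | .09 |
| 0.5 | .5 | 0.125 | .140 | .15 |
| 0.8 | .5 | 0.20 | .146 | .28 |

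Regression simulation of the same set-up agrees: about .08, .14 and .27 for the last three rows. The unadjusted test stays at about .05.

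**5. Direction.** Take a total effect of .426, none of it through contacts, with a = .3 and a trait that loads .5 on contacts. The bias is .3 × .5 × .5 = .075. A trait that raises contacts and improves outcome by .5 (motivation) pulls the estimate down to about .35. One that raises contacts and worsens outcome by .5 (severity) pushes it up to about .50. The true total and direct effects are both .426.

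**The case against.** - **The contacts covariate may not be the mediator.** Aim 1 speaks of contacts with other service providers, the mediator list of service contacts from a log. The wording is close but not identical, and Aim 1 gives no time window. Contacts could conceivably be a baseline measure, since baseline service connection is an Aim 3 moderator. But Aim 1 does not say baseline and pairs contacts with sessions, whereas Aim 3 does say baseline. Sessions alone would sustain the point.
- **Intent to treat may only mean analysing everyone as randomised.** The phrase is used once and not defined, and covariates do not breach that narrow sense. This stands as a point of wording. The substance is unaffected: the coefficient is not the total effect of assignment, which is what Aim 1 asks about.
- **The sizes are assumed.** This stands. The mediated shares, the arm shifts and the trait loadings come from no document, and the null calculation uses a single outcome rather than a five-wave growth model. If the arms end with equal sessions and contacts, the distortion disappears; at a 0.2 SD shift it is small. But the plan predicts a difference, and the efficacy analysis should not be valid only if that prediction fails.
- **The adjustment separates housing from service dose.** That is a question of mechanism, and Aim 2 already addresses it.

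**Conclusion.** The concern holds and should be fixed before the growth-model results are used as efficacy results. The error is structural: a primary efficacy model conditions on variables that arise after randomisation, at least one of which the plan appears to treat elsewhere as part of the effect.

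The size cannot be fixed from the documents. On the assumed paths above, 14% to 54% of the effect is removed and power falls from .86 to between .78 and .33. In the null case, type I error runs from about .07 to .28, depending on the shift and the loading. The sign of the bias depends on which unmeasured trait dominates.

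The finding is confined to the growth models: % days opioid use, the continuous secondary outcomes, and the Aim 3 interactions built on them. The discrete-time survival model for time to OUD is described with the condition contrast only and is not affected.

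**What to change.** Delete the sentence on session and contact covariates from Study Aim 1. State that the primary growth models contain condition and, if wanted, pre-randomisation covariates only. Keep sessions and service contacts for the Aim 2 mediation models, or for a dose analysis labelled exploratory. The Aim 3 growth models should follow the same rule.

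Optional additions are the urn balancing variables, which the documents do not name and the sponsor would have to list, and three indicators for the four advocates, who are crossed with condition. If advocate terms are used, the plan should say when advocates are assigned. Neither addition is needed to cure the defect.

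The cost is wording, with no new data. The power statement needs no change on this account, since it names only the condition contrast as predictor. The document is dated 6/28/2024 and is partly in the past tense, so the change should be a dated, justified amendment that says whether outcome results by arm had been seen. If adjusted results already exist, report them as supplementary beside the unadjusted ones.

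### The Aim 2 serial mediation models claim a time order between social and individual resources, but the plan gives the two mediators no separate visits and adjusts only for baseline values

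*Combined protocol and SAP*

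**What the plan says.** The Overview of Design states that "follow-up assessments will be completed at 3, 6, 9 and 12 months post-baseline".

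Study Aim 2 of the Statistical Analysis Plan begins with models that take a primary or a secondary mediator "assessed at the 3- or 6-month follow-up mediates the association between intervention and outcome at 6-month and 9/12-month follow-up, respectively". It then adds serial models containing both kinds of mediator, cites Figure 1 for them (not reproduced in the available text), and gives their purpose as "to test whether intervention first affects social resources, which then lead to changes in individual resources and subsequent outcomes". The adjustment rule is that "the baseline assessment of the mediators and outcomes will be controlled for in the analysis". No sentence says which visit supplies the first and which the second mediator in a serial model.

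The mediator list puts service contacts (from a service log), working alliance, social support and victimization in the primary group. Stress and self-efficacy are in the secondary group, with stress measured as "self-reported stress score (Cohen's PSS), and physiological hair cortisol level". The Statistical Power Analysis section gives power of .82 for the two-mediator serial model and .93 for the one-mediator model.

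**The concern.** The hypothesis under Specific Aim 2 is that social resources move first and activate individual resources, which then improve outcomes. A serial indirect effect supports this only if the data can tell that order from its reverse. If both mediators come from one visit, the direction of the arrow between them is an assumption of the model. If they come from successive visits but the earlier level of the second mediator is left out, its persistence over time can pass for an effect of the first.

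At stake is the mechanism conclusion. A significant serial effect could be reported as evidence that service contact and support reduce stress or raise self-efficacy when the reverse is true. Leaving the visits open also allows them to be chosen after the data are seen. The Aim 1 efficacy comparison is not affected.

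**Working it through.** **1. The plan's own figure.** The power of .82 cannot be uniquely reproduced, because no path values are given for Aim 2. It is plausible. With 240 participants, two-sided .05 (assumed), a mediator-to-outcome path of 0.30 and a standardised intervention path of 0.22, simulated one-mediator power is about 0.93. Adding a mediator-to-mediator path of 0.20 gives serial power of about 0.79. Over intervention paths of 0.14 to 0.25, mediator-to-mediator paths of 0.14 to 0.30, and 240 or 204 participants, serial power runs from 0.26 to 0.97. The concern is therefore not with the power figure.

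**2. Which visit sequences are strictly ordered.** The requirement is social before individual before outcome, using the plan's 3- and 6-month mediator visits.

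| Outcome | Ordered sequence |
|---|---|
| 6 months | none; the mediators share month 3, or the second shares month 6 with the outcome |
| 9 months | 3, 6, 9 |
| 12 months | 3, 6, 12 |

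**3. Why one visit cannot show direction.** With the same covariates, the t statistic for social in a regression of individual on social is identical to that for individual in a regression of social on individual. Both depend only on the partial correlation. The middle link is equally significant under either order.

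**4. Illustration with the order reversed.** From the plan: 240 × (1 − 0.15) = 204 completers (the 15% is stated for the growth model). Assumed:
- condition coded 0/1, unit-variance baselines, stability 0.5, residual SD √(1 − 0.25) = 0.866;
- housing raises the individual resource by 0.45;
- the individual resource raises the social resource at the same visit by d = 0.2, 0.3 or 0.4;
- only the individual resource affects the outcome (0.3);
- direct housing effect on the social resource c = 0 or 0.3.

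The test is that all three links of the planned chain have two-sided p < .05, standing in for the plan's bootstrap. Rates at which the false chain is significant, 3,000 runs per setting:

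| Specification | c = 0 (d = 0.2 / 0.3 / 0.4) | c = 0.3 (d = 0.2 / 0.3 / 0.4) |
|---|---|---|
| Both mediators at one visit | 8 / 19 / 26% | 69 / 88 / 92% |
| 3 then 6 months, baseline-only adjustment | 2 / 8 / 17% | 20 / 41 / 62% |
| 3 then 6 months, plus 3-month individual value | about 1% | 4 to 5% |

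Monte Carlo error is at most √(0.25/3000) = 0.9 points. Repeat runs moved entries by up to about two points.

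**5. Hand check.**
- First link: the total housing effect on the social resource is c + 0.45d. That is 0.09 to 0.18 when c = 0 and 0.39 to 0.48 when c = 0.3. The standard error with 102 per arm is 0.866 × √(1 + d²) × √(2/102), or 0.12 to 0.13. The ratios are about 0.7 to 1.4 and 3.2 to 3.7, which explains the gap between the columns.
- Middle link, staggered, baseline-only: the true effect is zero, but the coefficient has expectation 0.5 × d/(1 + d²). That is 0.5 × 0.2/1.04 = 0.096 for d = 0.2 and 0.5 × 0.4/1.16 = 0.172 for d = 0.4.
- Middle link with the 3-month individual value added: the expectation is zero, so this link is falsely significant in 5% of trials at most, in either direction. About half of those, roughly 2%, have the hypothesised sign.

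**The case against.** The strongest reply is that the text does not commit the serial models to a flawed layout. The visit pairing belongs to the one-mediator models, the serial models are introduced afterwards without visits, and Figure 1 may show staggered waves. This stands. A reader might infer that the plan takes both mediators from the same visit for every outcome, or that the serial hypothesis cannot be tested at all. The documents support neither reading: a 3-, 6-, then 9/12-month sequence is available. What Figure 1 cannot change is that only one visit precedes a 6-month outcome. Staggering alone also does not cure the problem if adjustment stops at baseline.

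Second, service contacts come from a log and might be counted over a period before the 3-month visit. The documents do not say whether entries are dated. This could order that one mediator; the text describes no such option for working alliance or social support.

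Third, the rates depend on assumptions. With no direct housing effect on the social resource they are much lower, and with one, the first link is genuine and only the direction between the mediators is false. Both are true, so both columns are shown. A direct effect is not contrived, since the plan expects housing to improve both kinds of resource.

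Finally, a reader might infer that "physiological hair cortisol level" makes matters worse because hair reflects a past period. The documents give no collection visits, segment length or period covered, so nothing here rests on it.

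**Conclusion.** The concern holds in limited form. The plan claims to test an order, does not assign the mediators to ordered visits, and states an adjustment that leaves the order unprotected. For 6-month outcomes, strict order among visit-measured mediators is impossible under the schedule. For 9- and 12-month outcomes it is achievable, but only with staggered mediators and the 3-month individual value in the model.

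The direction of the problem follows from the visit schedule and the symmetry of partial correlation. Its size is illustrative: false-chain rates of about 8 to 92% at one visit and 2 to 62% with staggering and baseline-only adjustment, against 5% or less when fully adjusted. These rest on the assumed paths, stability of 0.5 and two-sided .05. This is a change worth making to a secondary, mechanistic aim; it does not bear on the trial's main efficacy conclusion.

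**What to change.** In Study Aim 2, specify the serial chain as condition, social resource at 3 months, individual resource at 6 months adjusted for its baseline and 3-month values, and outcome at 9/12 months. Keep the baseline adjustment for the other variables. State the period over which service contacts are counted, and make Figure 1 agree with the text. Either omit serial models for 6-month outcomes or label their results as concurrent association that does not test order.

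The cost is SAP wording; the assessment visits needed are already scheduled. Confirm that hair cortisol is collected at the visits used, since the documents do not say. The ordered claim would be confined to 9/12-month outcomes, and the serial power of .82 must be re-simulated for this specification and may be lower.
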